- 2) Individuals with no risk factors in terms of general health status
- 3) Individuals whose complete upper jaw prosthesis has been made and delivered with known methods, whose controls have been completed, who have been using the delivered prosthesis for 3 months and whose tissues supporting the prosthesis are healthy

Exclusion Criteria;

- 1) Not accepting to participate in the study voluntarily after reading the voluntary consent form
- 2) Individuals with allergic reactions to the measurement materials planned to be used
- 3) People with systemic disorders or excessive weight loss that may occur for different reasons or dimensional changes that may occur in the tissues supporting the prosthesis due to other reasons

Sample Size and Power Analysis

PS Version 3.0 package program was used in this study. $\Delta=0.50$, $\alpha=0.05$, power of the test $1-\beta=0.80$, correlation between repetitions $\rho=0.20$ were assumed and the minimum sample size was accepted as 15. However, since working with a larger sample reduces the level of bias, it is desirable to work with as many patients as possible.

Randomization

The study was planned as a clinical study. The six different impressions planned for the edentulous upper jaw will be completed in two sessions, and the groups of impressions taken in the first and second sessions will not change. Three different groups of impressions to be taken in each session will not be subjected to randomization.

Blinding

Double blinding will be applied in the study.

1. Blinding of the evaluating researcher: The researcher will not learn which group the obtained data belongs to until the end of the evaluations.
2. Blinding of the researcher performing statistical analysis: The researcher will not learn which group the obtained data belong to until the end of the evaluations.

Data Collection (Primary Data - Secondary Data)

Primary Data:

Primary data will be collected for each case in the form of "STL" format obtained by exporting all maxillary complete edentulous jaw impressions of that case. These data will be overlaid with the help of a computer software (Geomagic design X version 2016.1.0, 3D Systems Inc. Rock Hill, SC), the fK and dD groups will be compared with each other and the differences between the groups will be recorded quantitatively.

Secondary Data:

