Secondary data will be determined by an evaluation scale asked to the patient to assess patient comfort, taste, nausea, burning sensation after the completion of each measurement. By analyzing the questionnaires and evaluation scales, the opinions of the patients about different measurement methods will be compared.

Statistical Evaluation

In the study, SPSS 20 package program will be used for data analysis. In the analysis of the study, first of all, Kolmogorov Smirnov adaptation test and Shapiro-Wilk test will be used to check whether the data have normal distribution. Afterwards, parametric or non-parametric statistical methods will be used to evaluate whether there is a difference (it is foreseen that independent and dependent group tests, chi-square test, Anova test, and graphs will be given if appropriate). When evaluating the results of the tests, the significance level will be taken as $\alpha=0.05$ and the results will be interpreted according to this critical value.

“Tam Dişsiz Üst Çenede Farklı Ölçü Yöntemlerinin In-Vivo Olarak Karşılaştırılması”

-VAS SKALASI-

Aşağıdaki parametreleri alınan ölçü sırasındaki değerlendirmenize göre 1 ile 10 arasında puanlayınız.

- Ölçü sırasındaki **konfor seviyenizi** değerlendiriniz.

- Ölçü materyalinin oluşturduğu **tat hissini** değerlendiriniz.

- Ölçü materyalinin oluşturduğu **bulantı hissini** değerlendiriniz.

- Ölçü alımı sırasında ağızdaki **yanma hissini** değerlendiriniz.

- Bundan sonraki dental ölçü işlemleriniz sırasında hangi ölçü tipini tercih edersiniz?

Geleneksel ölçü yöntemi

Dijital ölçü yöntemi

REFERENCES

2. Čelebić A, Knezović-Zlatarić D, Papić M, Carek V, Baučić I, Stipetić J. Factors Related to Patient Satisfaction With Complete Denture Therapy. *The Journals of Gerontology: Series A*. 2003;58(10):M948-M53.
3. Cooper LF. The current and future treatment of edentulism. *Journal of Prosthodontics: Implant, Esthetic and Reconstructive Dentistry*. 2009;18(2):116-22.

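### Two normality tests on a small sample choose between parametric and rank methods, with no rule for disagreement and no named within-patient test for the six impressions

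*Combined protocol and SAP*

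**What the plan says.** Section 3, Statistical Evaluation, starts with a distribution check: "Kolmogorov Smirnov adaptation test and Shapiro-Wilk test will be used to check whether the data have normal distribution". The choice of method follows from it: "Afterwards, parametric or non-parametric statistical methods will be used to evaluate whether there is a difference". The candidate tests are given only as a forecast: "it is foreseen that independent and dependent group tests, chi-square test, Anova test, and graphs will be given if appropriate". None of them is tied to an outcome, and no rank test is named. For the error level, "the significance level will be taken as $\alpha=0.05".

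Under Sample Size and Power Analysis, "the minimum sample size was accepted as 15", with "power of the test $1-\beta=0.80" and "correlation between repetitions $\rho=0.20". The number is a floor: "it is desirable to work with as many patients as possible". Materials and Methods makes the comparison within-patient, since every patient receives all six impressions and no patient groups are formed.

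**The concern.** Four things are left open:

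- which normality test decides when the two disagree, or when only some of the six methods fail;
- whether the tests are applied to each method's raw values, to within-patient differences or to model residuals (a paired design needs normality of the last two, not of the raw values);
- which form of the Kolmogorov-Smirnov test is meant, corrected for an estimated mean and SD or not;
- which test then compares the six methods.

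The data therefore choose the analysis, and with it the quantity being compared (means or ranks). If the two routes can lead to different conclusions, the result can be argued either way afterwards. A preliminary test on about 15 values is also a weak guide: it rejects some truly normal data by chance, and six repetitions raise that chance.

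**Working it through.** **Inputs from the plan.** Minimum of 15 patients, six methods, correlation 0.20, α = 0.05, power 0.80, difference 0.50 with no SD stated.

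**Assumptions.** Two-sided testing; each method tested separately by Shapiro-Wilk and by Kolmogorov-Smirnov with Lilliefors correction, each at 5%; any rejection sends the comparison to the Friedman test, otherwise repeated-measures ANOVA is used; one method differs from the other five.

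**Step 1. The plan's own 15, and the effect size it implies.** For a paired t-test, SD of the difference = SD × √(2(1 − ρ)) = SD × √1.6 = 1.265 × SD. With SD = 1 the test needs 53 patients. With SD = 0.508, the SD of the difference is 0.643, the standardised difference is 0.50/0.643 = 0.78, and 15 patients give 80% power. In units of the single-measurement SD the effect is 0.50/0.508 = 0.98. This value is solved backwards from the 15; the plan does not state it.

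**Step 2. How often truly normal data are switched.** For one test at 5% on six nearly independent methods: 1 − 0.95^6 = 0.265. Simulation gives 26–27% for Shapiro-Wilk alone and 38% when either test may trigger the switch.

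**Step 3. How often the two tests choose opposite routes.** If each test rejects somewhere in 0.265 of trials and either does so in 0.38, both do so in 0.265 + 0.265 − 0.38 = 0.15. Exactly one does so in 0.38 − 0.15 = 0.23. Simulation gives 22–23%. For a single method the tests disagree in only about 5% of cases with normal data. If the uncorrected Kolmogorov-Smirnov test is used, it almost never rejects at this size (0–4% per method). Its route then differs from that of Shapiro-Wilk in 26% of trials with normal data and in 62–92% with non-normal data.

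**Step 4. Power at a 0.98 SD shift (simulation, 3,000–4,000 trials per scenario).**

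| Data | Fixed model | Gate | Friedman |
|---|---|---|---|
| Normal | 84.5% (Huynh-Feldt 83.6%) | 80.4% | 72.6% |
| Lognormal, log SD 0.5, multiplicative shift up | log scale 84.8% (Huynh-Feldt 84.0%) | 73.8% | 73.1% |
| Lognormal, log SD 0.5, additive shift | log scale 93.3%; raw scale 83.9% | close to Friedman | 90.7% |
| Lognormal, log SD 0.5, multiplicative shift down | raw scale 65% (Huynh-Feldt 58%) | 71% | – |

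- Normal data: the gate loses 84.5 − 80.4 = 4.1 points. Two further sets of runs give 83.7 − 79.9 = 3.8 and 83 − 80 = 3.
- Skewed data are switched in about 96% of trials, so the gate is nearly the Friedman test. Against the log-scale model it loses 93.3 − 90.7 = 2.6 points with an additive shift and 84.0 − 73.8 = 10.2 with a multiplicative one (Huynh-Feldt). Other comparisons of that last case give 11 to 12.
- Against raw-scale ANOVA with skewed data the rank route can win: 90.7 − 83.9 = 6.8 points (Friedman) and 71 − 65 = 6 points (gate) in the last two rows.

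**Step 5. Error control.** Null rejection rates were 3.8–5.1% in one set of runs and about 4–5.6% for the two-stage rule in another.

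**Step 6. Does the route matter to the conclusion?** With a true effect, the Friedman test and Huynh-Feldt ANOVA reach opposite verdicts in about 14–25% of trials.

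**The case against.** There are four good arguments in favour of the plan.

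1. Type I error is intact, so no false-positive problem has been shown. This stands.
2. A reader might infer that the gate costs about 11 points of power. That is not supported as a general statement. With normal data it is the loss once a switch has happened (84.5 − 72.6 = 11.9). The procedure as a whole loses 3–4 points, because only about 38% of trials switch. Against the more conservative Greenhouse-Geisser ANOVA (78.4%), the Friedman test (73.1%) loses about 5 points and the gate (79.9%) loses nothing. With skewed data, 11 points needs lognormal distances, a purely multiplicative shift and a log-scale comparator that the plan does not mention. This stands.
3. A reader might also infer that the rank route is always the poorer one. Step 4 shows otherwise for raw-scale ANOVA on skewed data. Much of the cost under skew comes from not taking logs rather than from the gate itself. This stands too.
4. The statistical analyst is blinded to group (Blinding section), which limits steering towards a favoured method. This stands only in part: a blinded analyst can still see both sets of results before choosing a route, and blinding does not say which normality test decides.

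Per-method testing, switching on any rejection, the Friedman test and an unsigned metric are all readings that the plan does not state. The rates above depend on them.

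**Conclusion.** The point holds as a gap in pre-specification with a modest price. The plan lets two normality tests on a small sample select the analysis, without a deciding rule and without a named within-patient test for the six methods. Under the stated assumptions, truly normal data are sent to a rank test in about 38% of trials, and the two checks point in opposite directions in about 23%. The expected power cost is about 3–4 points with normal data. With skewed distances it is about 2–10 points against a log-scale model, the upper end being the case most favourable to that model.

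The documents do not support saying that the gate invalidates the error rate, or that it always costs power. The power figures rest on exactly 15 patients, correlation 0.20 and the back-solved 0.98 SD effect; more patients or a different effect would change them. The absence of a deciding rule depends on none of these.

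**What to change.** Remove the normality tests as a decision rule and name one primary analysis for the scan deviations before the data are seen:

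- a repeated-measures or mixed model with patient as random effect and method as fixed effect, with Huynh-Feldt or equivalent correction;
- on log deviation if the metric is unsigned and on raw deviation if it is signed, with the metric itself stated;
- residual checks reported as description only, with no effect on the choice of test;
- the Friedman test reported as a sensitivity analysis.

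For the 1–10 patient scales, specify the Friedman and Wilcoxon signed-rank tests whatever any normality test shows.

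Naming a different single within-patient test in advance, including Friedman, would also close the gap in pre-specification. The model is preferred because it had more power than the gate in the scenarios compared, except that Greenhouse-Geisser correction removes its advantage with normal data.

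The cost is a few sentences in Statistical Evaluation, and SPSS 20 can fit the model. The one drawback is that log-scale results are ratios of geometric means and need a sentence of explanation in the report.

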statistical difference was found. It has been shown that edentulous jaws can be recorded with direct digital impressions similar to conventional impression methods and that these impressions can be used clinically in the production of tissue-supported removable prostheses (15).

Chebib et al. compared the accuracy of different impression techniques in patients with maxillary complete edentulism in a clinical study. Twelve patients participated in the study and a total of five impressions were taken from each patient. In the ALG group, impressions were taken with a stock-tray and irreversible hydrocolloid impression material. In the ZOE group, individual tray borders were shaped with impression compound and impressions were taken with ZOE material. This group was also considered as the control group. In the PVS group, individual tray and medium-viscosity polyvinylsiloxane impression material were used. In the PVSM group, the inner surface of the impression taken in the PVS group was modified with ZOE impression material. All analog measurements were digitized with the same laboratory scanner. In the TRI group, scanning was performed with an intraoral scanner after the reference points created with composite on the maxillary soft tissue. Then, with the help of a software, the scan data were matched in a best-fit manner. As a result of the study, PVS, PVSM and TRI groups showed similar deviations and were found clinically acceptable. Irreversible hydrocolloid impression material was shown to be contraindicated for the final impression of the complete edentulous maxilla (16).

There is limited information on the comparison of the direct digitalization method used in the impression of edentulous arches with traditional impression methods and there is a need for improvement. Given this situation, the aim of this study was to expand the existing knowledge for direct digitalization in the edentulous maxilla by comparing six different edentulous arch impressions.

3) Materials and Methods:

In this study, it was planned to compare a total of six different permanent impressions obtained from patients with complete edentulous maxilla using three different conventional impression methods and three different digital impression techniques. Patient grouping was not planned in the study, and it was decided to take impressions from each patient who met the inclusion criteria under conventional and digital groups.

Physical Record (fK)=

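### Results are read only by whether p crosses 0.05, with no confidence interval, so a non-significant scan-versus-conventional comparison could be taken as similarity

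*Combined protocol and SAP*

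**What the plan says.** Statistical Evaluation (under 3, Materials and Methods) plans normality checks, then parametric or non-parametric tests for a difference. Alpha is 0.05, and "the results will be interpreted according to this critical value". This is the only interpretation rule in the document. No confidence interval, equivalence or non-inferiority margin, or rule for a non-significant result appears anywhere.

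Sample Size and Power Analysis lists a difference of 0.50, alpha 0.05, power 0.80 and a correlation between repetitions of 0.20. These "were assumed and the minimum sample size was accepted as 15". The section gives no SD, and no unit or outcome for the 0.50. It would welcome a larger sample but sets no number.

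Data Collection says that differences between the conventional and digital records will be captured as numbers. It does not plan to report their precision or give them a part in the interpretation.

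The background section (2, Importance of the Project) describes an earlier clinical comparison of scans with conventional impressions. It reports that no "statistical difference was found. It has been shown that edentulous jaws can be recorded with direct digital impressions similar to conventional impression methods".

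**The concern.** A test for a difference can give evidence that two methods differ. When it is non-significant, it does not by itself show that they are alike: the true difference may be small, or the study may have been too imprecise to see it. Only the interval around the estimate separates these cases, and the plan does not ask for one.

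The practical question for readers is whether a direct scan of the edentulous upper jaw can stand beside a conventional impression. If a comparison misses significance, nothing in the plan prevents it from being reported as showing that the methods are similar. The background section places a non-significant result and a conclusion of similarity side by side in just this way. At stake is a conclusion about digital impressions that could rest on lack of precision.

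**Working it through.** **Inputs from Sample Size and Power Analysis:** difference 0.50, alpha 0.05, power 0.80, correlation 0.20, n = 15.

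**Assumptions:** a two-sided paired t-test, since every patient receives all six impressions and sidedness is not stated. The per-method SD is not given, so a range of 0.3 to 1.0 is shown.

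**Step 1: the plan's own figure.** The 15 cannot be derived from the printed inputs because the SD is missing.
- With an assumed SD of 0.50, the paired t-test needs exactly 15 patients (power 0.81).
- If 0.50 is in SD units (SD = 1), it needs 53, and 15 patients give power 0.30.
- Solving backwards, exactly 80% power with 15 patients needs a standardised paired difference of 0.778. The SD of the difference is then 0.50 / 0.778 = 0.643, and the per-method SD is 0.643 / √(2 × (1 − 0.20)) = 0.643 / 1.265 = 0.508.

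**Step 2: formulas.**
- SD of the paired difference = SD × √(2(1 − 0.20)) = 1.265 × SD.
- 95% half-width = 2.145 × SD of difference / √15 (t with 14 df).
- Chance of a non-significant result at a true 0.50 = 1 − power, from the noncentral t with noncentrality 0.50 × √15 / SD of difference.
- Largest difference compatible with a just non-significant result = 2 × half-width, because the estimate then lies about one half-width from zero.

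At SD 0.508 the half-width is 2.145 × 0.643 / 3.873 = 0.356, and twice that is 0.71.

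**Step 3: results for n = 15.**

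| SD per method | SD of difference | 95% half-width | Non-significant at true 0.50 | 2 × half-width |
|---|---|---|---|---|
| 0.3 | 0.379 | 0.21 | 0.3% | 0.42 |
| 0.4 | 0.506 | 0.28 | 5.5% | 0.56 |
| 0.508 | 0.643 | 0.356 | 20% | 0.71 |
| 0.6 | 0.759 | 0.42 | 34% | 0.84 |
| 0.8 | 1.012 | 0.56 | 57% | 1.12 |
| 1.0 | 1.265 | 0.70 | 70% | 1.40 |

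**Step 4: what the interval adds.** At SD 0.508, an observed difference between 0.50 − 0.356 = 0.14 and 0.356 is non-significant while its interval still contains 0.50. At SD 0.3, every non-significant result excludes 0.50, because 0.50 − 0.21 = 0.29 exceeds 0.21. At SD 1 the half-width exceeds 0.50, so at the expected standard error every non-significant result includes a difference of size 0.50 in one direction or the other. The p-value rule treats these three situations alike.

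**Step 5: would 15 patients support a formal similarity claim?** Suppose similarity required the 90% interval to lie within ±0.50, and the true difference were 0. The chance of success is 95% at SD 0.4, 78% at SD 0.508, 57% at SD 0.6, 19% at SD 0.8 and 4% at SD 1. The answer depends almost wholly on the unstated SD.

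**The case against.** **The plan states no similarity aim.** This is correct. Its aim is to extend knowledge by comparing six impressions, and its tests look for a difference. A reader might infer that the trial will claim equivalence from a non-significant result, but no sentence says so. The background passage summarises a cited study and is not this trial's decision rule. Elsewhere the same section is cautious, treating the evidence on one-stage against two-stage impressions as inconclusive. What stands is that the plan leaves the misreading open and its own background shows how it could arise.

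**The 20% is circular.** It is: the SD was solved to give 80% power, so 20% is the plan's own beta. A reader might infer that 15 patients is the wrong number. The documents do not support that, because 15 fits an SD of about 0.50 and is called a minimum. A 20% miss rate is ordinary for detecting a difference. The objection does not reach the missing interval, which is needed at any sample size.

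**The planned 0.50 could serve as an equivalence limit, so that the same 15 patients could prove similarity.** This reading is tempting but unsupported. The 0.50 was set as a difference to detect, has no unit or outcome, and is nowhere justified as an acceptable discrepancy. Step 5 shows that success could be as low as 4%.

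**The outcome may not be a signed difference.** If the overlay yields an unsigned deviation between two surfaces, a mean difference centred on zero does not apply directly. This stands, and the sponsor must define the outcome.

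**Conclusion.** The concern holds as a gap in interpretation and reporting: the plan has one rule, no interval, and no guard against reading non-significance as similarity. How often this would mislead is unknown, because the SD is not stated; the range in the table assumes a two-sided paired t-test, a correlation of 0.20 and exactly 15 patients. More patients would narrow the intervals and lower the risk. The finding does not show that the sample size is wrong, that the trial will claim equivalence, or that ±0.50 is a suitable margin. The change should be made, and its value does not depend on which SD is true.

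**What to change.** Replace the last sentence of Statistical Evaluation with wording such as:

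> Each within-patient comparison of a scan method with a conventional impression is reported as the mean difference (or the Hodges-Lehmann median difference if the analysis is non-parametric) with its 95% confidence interval. A non-significant result is not described as similarity or equivalence. If its interval includes the planned difference of 0.50 in either direction (unit and outcome to be stated), it is reported as inconclusive.

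The sponsor must state the outcome and unit to which 0.50 refers. If the overlay gives an unsigned deviation, the sponsor must also state the quantity being estimated, so that the interval and the 0.50 refer to the same scale.

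A formal equivalence rule based on a 90% interval should be added only if the sponsor justifies a margin before unblinding. The 0.50 should not be adopted for this by default.

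The cost is a few sentences and some extra lines of output, with no new patients or procedures. The downside is that some results now reported as no difference become inconclusive, possibly most of them if the SD is near 1.

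### The patient form, as printed, gives no meaning for 1 or 10 on its four scored items, so reversed scores can shrink the method differences on those secondary items

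*Combined protocol and SAP*

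**What the plan says.** The form at the end of the protocol is headed as a VAS scale. Its instruction is "Aşağıdaki parametreleri alınan ölçü sırasındaki değerlendirmenize göre 1 ile 10 arasında puanlayınız": score the parameters below from 1 to 10 according to your assessment during the impression. Four scored items follow:

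- Comfort: "Ölçü sırasındaki konfor seviyenizi değerlendiriniz"
- Taste: "Ölçü materyalinin oluşturduğu tat hissini değerlendiriniz"
- Nausea: "Ölçü materyalinin oluşturduğu bulantı hissini değerlendiriniz"
- Burning: "Ölçü alımı sırasında ağızdaki yanma hissini değerlendiriniz"

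Each item only asks the patient to evaluate the named level or sensation. None attaches words to 1 or 10. A fifth item asks whether the patient would prefer conventional or digital impressions in future.

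Secondary Data describes an "evaluation scale asked to the patient to assess patient comfort, taste, nausea, burning sensation after the completion of each measurement" and says that patients' opinions of the methods will be compared. Neither it nor Statistical Evaluation gives a direction, a reverse-coding rule, an explanation to be read to the patient, or a total score.

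**The concern.** A score can be interpreted only if its direction is known. Taste has no obvious direction: for an unpleasant material, a patient rating strength scores high and a patient rating pleasantness scores low. Comfort, nausea and burning do have an ordinary reading (more of the named thing is a higher number). However, comfort comes first and has 10 as the good end, and nausea and burning then have 10 as the bad end. With no printed labels, some patients may carry 10 = good down the page.

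These items are the study's only scored patient-reported data, and the planned minimum sample is small. A reversed score looks like any other number on the form, so it cannot be reliably identified afterwards.

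**Working it through.** **Inputs from the documents.** The scale runs from 1 to 10 (the form). Every patient receives all six impressions (Materials and Methods). The minimum sample is 15 (Sample Size and Power Analysis).

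**Assumed inputs.** The share p who reverse, the true difference δ and the SD of the paired difference σ are assumptions. The documents give none of them for this scale.

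**The plan's own figure.** The 15 is stated with Δ = 0.50, α = 0.05, power 0.80 and ρ = 0.20, but without an SD, units or outcome. For a two-sided paired t-test, the SD of the difference is SD × √(2 × (1 - 0.20)) = SD × 1.265. If SD = 0.5, this is 0.632, the standardised difference is 0.50/0.632 = 0.79, and 15 patients give 81.2% power. If SD = 1, 53 patients are needed. So 15 can be reproduced under one assumption, but it says nothing about the patient scale. It is used below only as a number of patients.

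**Step 1: one reversed patient.** Reversal replaces x by 11 - x. For methods A and B the difference becomes (11 - a) - (11 - b) = -(a - b). The constant drops out and the sign flips, so comparing within patients gives no protection.

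**Step 2: the whole sample.** The mean becomes (1 - p)δ + p(-δ) = (1 - 2p)δ. The mean square stays at σ² + δ², so the variance becomes σ² + δ² - (1 - 2p)²δ². The mean falls while the variance rises.

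**Step 3: numbers.** Illustration A assumes δ = 2 and σ = 2.5, so σ² + δ² = 6.25 + 4 = 10.25. At p = 10%, for example, the mean is 1.6 and the SD is √(10.25 - 2.56) = 2.77. Illustration B sets δ/σ = 0.78, which gives 80% power when nobody reverses. Power is simulated for a two-sided paired t-test with n = 15.

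| p | Factor (1-2p) | Mean (A) | SD (A) | Power (A) | Power (B) |
|---|---|---|---|---|---|
| 0 | 1.00 | 2.0 | 2.50 | 82% | 80% |
| 5% | 0.90 | 1.8 | 2.65 | 69% | 67% |
| 10% | 0.80 | 1.6 | 2.77 | 55% | 53% |
| 20% | 0.60 | 1.2 | 2.97 | 32% | 31% |
| 30% | 0.40 | 0.8 | 3.10 | 16% | 16% |
| 50% | 0 | 0 | 3.20 | not run | 5% |

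**Step 4: direction changing from form to form.** If each form is reversed independently with probability p, the factor is again (1 - 2p). With assumed means of 8 and 6, SD 2.03 and correlation 0.20, power falls from 80% to 48% at p = 10% and 27% at p = 20%. With means of 9 and 7.5 and SD 1.52, the figures are about 35% and 17%.

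**Step 5: chance of any reversal.** At p = 10%, the chance that at least one of 15 patients reverses is 1 - 0.9¹⁵ = 0.79.

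**The case against.** **Lost graphic.** The strongest objection is that the labels may exist. A visual analogue scale is normally a line with labelled ends. In the text as read, the four scored items have no line, number row or blank, whereas the preference question keeps its two options. A scale graphic may therefore have been lost in extraction, which would not be an error in the plan. Against this, no missing-figure marker stands there and the written instruction is complete in itself. The objection makes the point conditional but does not remove it. Even with labels on the form, Statistical Evaluation would still give no direction.

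**Ordinary reading.** "konfor seviyenizi" asks for a level and "bulantı hissini" for a sensation, and most people would score more as higher. This stands. The ambiguity is greatest for taste, and nothing in the documents suggests that 10% to 30% of patients would reverse the other three items.

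**Detection.** Each patient is scored after each impression, and the two plain scans (AI off and AI on) use no impression material. Burning near 10 after a plain scan and near 1 after zinc-oxide eugenol would suggest reversal. This is a useful but imperfect check, and it does not settle what a patient meant by taste. The scale is also described as asked to the patient, so staff may explain it, but no explanation is documented.

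**Stronger readings that the documents do not support.** A reader might infer the following:

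- That method differences cancel. They do so only when 1 - 2p = 0, that is, when half the patients reverse.
- That mixing positive and negative items corrupts the result in itself. That would need an uncoded total score, and none is mentioned. The mix matters only as a prompt for response errors.
- That every secondary outcome is affected. The preference question is a choice between two categories and has no direction.
- That the power figures are this trial's loss. They rest on assumed inputs, 15 is a minimum, and no secondary item has a power target.

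**Conclusion.** The point holds in a limited form. As printed, the form defines neither end of its 1-10 scale, the analysis text gives no direction, and the taste item does not say what it measures. Reversed scoring is therefore possible and cannot be reliably recognised later. For complete reversal (11 - x), the factor (1 - 2p) is exact whatever the effect size or SD. Its value here is unknown because p is unknown. The power losses in the table show the mechanism in a small sample and do not measure harm in this trial. The effect is confined to the four scored secondary items; the primary STL comparison and the preference question stand apart. The conclusion depends on the form in use having no printed labels, which the sponsor can check at once.

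**What to change.** Before first use:

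1. Print labels at 1 and 10 on every item. For example: comfort, 1 = very uncomfortable and 10 = very comfortable; nausea and burning, 1 = none and 10 = severe.
2. Word the taste item as either pleasantness or strength, and label its ends to match (for pleasantness, 1 = very unpleasant and 10 = very pleasant).
3. State in Statistical Evaluation the direction of each item and that the items are analysed separately.

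The cost is reprinting a one-page form and notifying the ethics committee of the wording. No extra visits or patients are needed. If the form in use already carries labels, only the third step and any needed clarification of taste remain.
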